Persons affected by certain health conditions, including Alzheimer's disease, vestibular loss, stroke, and traumatic brain injury, as well as older adults and even some otherwise healthy individuals experience disorientation and disequilibrium. **One common type of dizziness reported across these populations is visually-induced dizziness**, which is triggered by visual stimuli such as busy patterns or moving scenes. The cause of visually-induced dizziness is believed to be **visual dependence**, a perceptual style that may be either developmental or acquired. Studying persons with this specific type of dizziness provides us unique opportunities to pursue our **long-term goals** to advance understanding of normal postural orientation and equilibrium, as well as the association between dizziness and falls.

The current standard of care for persons with visually-induced dizziness is optokinetic stimulation (repeated exposure to complex patterns and moving images). Though initial efficacy trials of this intervention were positive, results from subsequent effectiveness trials are less clear. This modality has also proven to be difficult to implement in practice due to a lack of clarity regarding treatment parameters, optimal delivery methodologies, and who will most likely benefit. As a result, use of optokinetic stimulation often results in exacerbation of symptoms and/or early withdrawal from treatment. Herein, **we introduce a promising intervention** based in part on sensory re-weighting theory and findings from preliminary work in primate and human models of bilateral vestibular ablation.

Our **central hypothesis** for this study is that intensive sensory re-weighting training will result in reduced visual dependence in healthy persons and those with visually-induced dizziness. In order to achieve this outcome, we developed these **specific aims** in the context of a phase I efficacy trial.

1. Assess the accuracy, sensitivity, and specificity of VR-based robotic verticality assessments. We will calculate the accuracy, sensitivity, and specificity of each verticality perception measure conducted while standing upright or tilted leftward or rightward in the frontal plane.

2. Determine the potential diagnostic value of IP, a postural equilibrium measure.

The IP curves of healthy persons and symptomatic persons will be significantly different (Hypothesis A).

3. Demonstrate the effects a novel sensory re-weighting intervention.

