The following patient-reported outcome measures will be collected through secure links to the ICTR REDCap database unless otherwise noted below (or on paper if participants decline to use email for study-related purposes):

Patient-reported Outcome Measures:

Visual Vertigo Analogue Scale (VVAS): Time Required: < 5 minutes. The original VVAS(2) consists of nine scales, each relating to a specific symptom-provoking situation. The distance from the zero anchor to the respondent's marking is measured to the nearest 0.5 cm. Items that are not applicable to the individual's life are completed as imagined. Internal consistency and validity of the VVAS have been established(2). A total score is calculated to determine the severity of visual vertigo by summing all items, dividing by the number of answered items, and then multiplying by 10. We will use the total score as the measurement variable for this instrument. The analysis metric will be the difference between pretest and post-test measurement within subjects and by group. These data will be collected at each assessment timepoint.

Vision-related Dizziness Questionnaire (VRD-25): Time Required: < 5 minutes. The VRD-25(3) is used to quantify vision-related dizziness. This outcome measure consists of 25 questions comprising two subscales [frequency (VRD-12) and severity (VRD-13) of symptoms]. Test-retest reliability for the VRD-25 is well above the good performance level and convergent validity for the VRD-25 was demonstrated with the DHI. Spearman correlation coefficients are 0.75 between the DHI and VRD-12 frequency scale and 0.76 between the DHI and VRD-13 severity scale(3). The analysis metric will be the difference between pre-test and post-test measurement within subjects and by group. These data will be collected at each assessment timepoint.

Dizziness Handicap Inventory (DHI): The DHI (4) is used to assess a person's perceived level of handicap stemming from symptoms of dizziness. This patient-reported outcome measure consists of 25 questions related to physical, emotional, of functional health. Each question is answered as "yes" (dizziness is always a factor), "sometimes" (dizziness is sometimes a factor), or "no" (dizziness is never a factor for a given situation or issue. Responses are scored as "yes" = 4 points, "sometimes" = 2 points, and "no" = 0 points. The maximum score on the DHI is 100 points with higher scores indicating higher levels of perceived handicap.

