Many questions that we are asking during the telephone screening are directly related to the potential participant's past medical history, past surgical history, medications, diagnoses, testing, and date of onset of symptoms. The screening is worded in such a way that allows the research team to ask follow-up questions. For example, screening questions 8 and 9 refer to medications. If the potential subject answers yes, then an appropriate follow up question from the screener is, "What medications do you take?" Additionally, certain questions refer to specific diagnoses. If the potential subject answers yes, then the logical questions that follow are, "What is your diagnosis? When did your symptoms start? How were you treated?" Depending on whether a patient has a surgical diagnosis or not, the screener might also ask, "What type of surgery did you have?" The REDCap database that we use to gather data has built in comment fields that allow us to record additional information as needed.

In anticipation that participants may not be able to provide accurate or complete information during the telephone screening process, we are requesting to access the Health Link records of participants these participants. [name] is a neurotologist and [name] is a board-certified specialist in neurological physical therapy who specializes in the management of persons with dizziness and balance disorders. Thus, these study team members have appropriate clinical access to Health Link. Only [name] or [name] were tohad access health records and only the health records of participants who are unable to provide complete and accurate information to the study team will be accessed. The only information that will be collected from these health records will be information that directly pertains to answering the questions posed during the telephone screening process.

Health record numbers will be collected from participants at the time of written, informed consent. This information will be entered directly into the REDCap and OnCore databases.

Data Collection Forms:

Data collection forms were developed in ICTR REDCap.

Data Management:

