Potential Psychosocial Risks: This study includes completing a telephone screening. The questionnaires and assessments used in this study are new but are like those that are common and currently in use in clinical practice. These activities are like and of no greater risk than activities of daily living or that would be encountered during a standard clinical examination. Positioning in the device is a mild version of what is experienced by patients in clinical tilt table or rotational chair testing. The sensory re-weighting training is similar treatment activities currently performed in the clinic in that it involves training of orientation and balance. None of these activities is expected to pose significant psychosocial risks; however, many patients with dizziness and/ falls also have symptoms of anxiety. Therefore, some participants could become anxious during testing and/or training.

Common Risks: Studies show these assessment and treatment techniques are safe, well-tolerated, and associated with relatively mild and infrequent adverse reactions(46-48). However, potential adverse events (AE) include vertigo (dizziness), nausea, vomiting, fear of falling, loss of balance, headache, joint pain, and muscle soreness. Dizziness is often associated with emotional distress, such as with fear of falling. Mild dizziness (self-reported intensity $\leq 3/10$) lasting ≤ 15 minutes is an expected,

temporary reaction; thus, only prolonged dizziness (>15 minutes) and/or severe dizziness (self-reported intensity \geq 7/10) will be reported as an AE. Imbalance is also expected with assessment. If a participant reports a prolonged (> 24 hours) of worsened symptoms, he/she will be advised to contact his/her primary care provider for guidance regarding managing symptoms and/or to discuss if continued participation in this research is advisable. Subjects could experience vasovagal syncope due to being relatively immobile in a standing posture for periods of time.

Serious Risks: Falls or any injury that occurs while performing tests or interventions will be reported as a serious adverse event (SAE).

Minimization of Risks:

The risk of vertigo, nausea, and vomiting will be minimized by:

1) stabilizing the participants in a comfortable harness,

2) limiting duration of exposure to visually provocative stimuli (<~5 s per trial),

3) verbally monitoring participant tolerance and comfort to the intervention,

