4) pausing the study for a rest break or terminating the study if symptoms don't resolve, and

5) allowing the participant to sit down with elevated legs within or outside the device during requested rest periods.

The risk of injury due to loss of balance will be minimized by:

1) recruiting participants that are independently ambulatory in the community,

2) providing physical assistance and handles to aid in negotiating the one 6 inch step up onto the device and the one step forward into position, and

3) placing the participant in a full torso harness attached to an overhead frame that prevents them from moving downward more than a few inches or tipping more than 30 degrees.

The risk of anxiety will be minimized by:

1) providing physical assistance stepping onto the device,

2) reassuring the participant that the safety harness will prevent any possible injury if they were not able to support themselves, and

3) guiding the participant through relaxation techniques as appropriate.

The risk of headache, joint pain, and muscle soreness will be minimized by:

1) ensuring that the participant is comfortable at all times via frequent verbal contact,

2) designing the device to be comfortable for all shapes and sizes of participants,

3) moving the person between postures (vertical, leaned left, leaned right) every 10 trials (~ approximately every 30 seconds), and

4) taking seated rest breaks as needed.

The risk of vasovagal syncope is minimized by:

1) asking about history of vasovagal syncope and excluding participants with frequent history (> 1/month),

2) reminding participants to move their legs every 10 trials,

3) using fan to provide gentle air flow for cooling and fresh air,

4) changing posture every 10 trials, and

5) frequently asking participant if they need a rest break or need to terminate the study.

The general risk of being restrained within a device is minimized by:

1) system design that allows the participant to be fully removed from all harness attachments within 5 seconds.

If patients experience a worsening of their condition during this study, they will be directed to contact their primary care provider for guidance. Participants will also be encouraged to consult with their primary care provider or prescriber in order to address any concerns related to withholding p.r.n. medications.

There is also a blood pressure cuff and water available in the lab. [name] is a physical therapy clinician and is trained in CPR and BLS.

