Justification of Risks: Study procedures are consistent with functional and environmental challenges participants face during normal activities of daily living. The information gained about a participant's dizziness and/or imbalance may help him/her overcome current functional limitations and activity restrictions. Risks of recommended withholding p.r.n. medications are no greater than those associated with self-withholding of these medications. By their nature, the p.r.n. medications in question for this research are not life sustaining.

Auditing: All SAE will be reported to the PI immediately. Participants who experience any AE and SAE will be encouraged to report these to their primary care physician. Participants experiencing these events were to be followed up and assessed by [name] or [name] as needed. ICTR OnCore will be used to document all AE and SAE. All AE will be reviewed by the study team on an as needed basis. Decision making regarding all AE and SAE will be reported in ICTR OnCore.

Provisions to Address Unanticipated Problems or Complications: The PI and [name] conducted continuous monitoring for unanticipated problems, AEs, and SAEs during each study visit. The PI or [name] also inquired about possible AEs and SAEs that may have occurred between study visits by asking patients to report any symptoms or concerns that may arise between or after study visits. As directed in the consent forms, participants will be advised to call either [name] or [name] if they have any questions or concerns about their participation in this research. Should a possible unanticipated problems, AE, or SAE be suspected, [name] will discuss the issue or event with Drs [name] and [name] who hold final decision-making authority. Health Sciences Institutional Review Board guidance for reporting unanticipated problems and adverse events will be followed. If an unanticipated problem, AE, or SAE necessitates follow up with a medical provider, participants will be given direction in accordance with the information in the consent forms.

Potential Benefits of Participating:

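### The adverse-event rule leaves out brief dizziness above 3/10 and below 7/10, although its stated reason covers only 3/10 or less, and the protocol does not say that these episodes are recorded or tabulated

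*Combined protocol and SAP*

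**What the plan says.** The rule stands in the combined protocol and SAP under Harms, Common Risks. Vertigo (dizziness) is the first item in the list of potential AEs. The text then takes up "Mild dizziness (self-reported intensity", sets its limits at 3/10 or less and 15 minutes or less, and calls it an expected, passing reaction. From this it concludes, with the word *thus*, that "only prolonged dizziness (>15 minutes) and/or severe dizziness" will be reported as an AE, and it sets severe at 7/10 or more.

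Two provisions depend on that definition. Under Auditing, "ICTR OnCore will be used to document all AE and SAE". Under Provisions to Address Unanticipated Problems or Complications, the team "conducted continuous monitoring for unanticipated problems, AEs, and SAEs during each study visit". The same paragraph adds three safeguards: participants are asked about any symptoms or concerns between or after visits, suspected events go to team members who make the final decision, and IRB guidance on reporting is to be followed. Feasibility and Contingency Plans promises guidance on modifying the intervention for participants who tolerate testing poorly.

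Statistical Methods covers demographic description, the three aims, missing data and correlations between outcomes. It contains no summary of AEs or tolerability.

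**The concern.** The reason given for the rule does not reach as far as the rule does. The reason covers mild, short dizziness. The rule also removes short dizziness of moderate intensity from the AE count, and nothing in the text says why.

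Provoked dizziness is a harm that the protocol holds against current care. Specific Aims says that use of optokinetic stimulation "often results in exacerbation of symptoms and/or early withdrawal from treatment". Background and Rationale adds that some patients are prone to adverse events with it, and states the belief that the new method will prove safer. A reader of the trial's report is therefore likely to look at how much dizziness the training provoked. Under the rule, a participant could reach 6/10 at each of the six training visits, recover within 15 minutes every time, and add nothing to the AE record. Such episodes are plausible, since one of the two groups is enrolled for visually-induced dizziness and participants are asked to avoid as-needed anti-vertigo medicines for 48 hours before visits.

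What is at stake is the completeness of the tolerability description.

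**Working it through.** **Step 1: which episodes fall between the reason and the rule.** All inputs come from Harms, Common Risks.

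- Called expected: intensity ≤ 3 and duration ≤ 15 minutes.
- Reportable as an AE: duration > 15 minutes and/or intensity ≥ 7.
- Left over (neither): intensity > 3 and < 7, with duration ≤ 15 minutes.

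The protocol does not say whether ratings are whole numbers. If they are whole numbers from 0 to 10 (an assumption), the grid is:

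| Intensity | 15 minutes or less | Longer than 15 minutes |
|---|---|---|
| 0 to 3 | expected, not an AE | AE |
| 4 to 6 | not called expected, not an AE | AE |
| 7 to 10 | AE | AE |

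The grid has 11 × 2 = 22 cells (rating 0 only completes it). AE cells: 11 + 4 = 15. Expected cells: 4. Left over: 22 − 15 − 4 = 3, namely ratings 4, 5 and 6 at 15 minutes or less.

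**Step 2: whether another stated provision records these episodes.**

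- *OnCore* documents what has been classed as an AE or SAE, so entry depends on the rule in Step 1.
- *In-visit monitoring* looks for unanticipated problems, AEs and SAEs. Staff could raise a moderate episode as an unanticipated problem, but no text tells them to.
- *Between-visit enquiry* has no intensity threshold and would bring some symptoms to light. Its stated purpose is to find possible AEs and SAEs, and it has no recording rule for anything less.
- *Referral of suspected events and IRB guidance* govern decisions and reporting. They do not create a record of sub-threshold symptoms.
- *Minimization of Risks* provides verbal checks of tolerance and "pausing the study for a rest break or terminating the study" if symptoms persist. These act on symptoms; no recording step is stated.
- *Tolerance guidance* in Feasibility and Contingency Plans is promised but not set out.
- *The device data file* (Data Collection Methods) names body measurements, date and time, and performance variables. Symptoms are not named.
- *Questionnaires* do not fill the gap. The VVAS has nine scales, "each relating to a specific symptom-provoking situation", so it does not rate episodes during a session. VVAS, VRD-25 and DHI are collected at four assessment timepoints (Table 3), and Table 2 shows training but no assessment in week 3.
- *Rest requests and adherence* (Criteria for Stopping a Round of Training; Definition of Adherence) leave an indirect trace of poor tolerance. No text says that the reason for a rest is noted.
- *Forms*: "Data collection forms were developed in ICTR REDCap", but they are not reproduced, nor is the protocol manual listed in Timeline for Study Completion. A symptom field may exist in either.

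**Step 3: whether the analysis would show them.** Statistical Methods plans no harms table. This omission applies to every AE, not only to the band in Step 1.

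**Size.** The protocol gives no rate of provoked dizziness, so no number of missed episodes can be derived.

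**The case against.** The best defence has four parts.

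First, the rule limits what is reported as an AE; it does not say that milder episodes go unrecorded. Applying it requires staff to ask about intensity and duration, and the forms are not in the document. This stands. A reader might infer that moderate episodes were in fact never recorded. The text supports only the narrower statement that no stated provision records them.

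Second, the safeguards are wider than the AE rule: an open symptom enquiry between visits, referral of suspected events, IRB guidance and promised guidance for poor tolerance. These weaken the concern. None of them states that sub-threshold episodes are written down or tabulated, so they do not remove it.

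Third, safety is not an aim, hypothesis or outcome. A reader might infer that the rule undermines a safety comparison with optokinetic stimulation. The documents do not support that: there is no optokinetic arm and no comparison is planned. The claim of being safer is a belief stated in the background, and a single-treatment study with 15 per group could not establish it under either AE rule.

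Fourth, a 7/10 cut-off for AEs is a defensible choice, exposure to provocative stimuli is limited to about 5 seconds per trial, and training shows only a rod in a void scene. This also stands. The cut-off itself is not the fault. The mismatch is between the cut-off and its reason, together with the lack of a stated record below it.

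**Conclusion.** The concern holds in a narrow form and is minor. Brief dizziness above 3/10 and below 7/10 is neither called expected nor reportable as an AE, no text in the document says that it is recorded, and no harms summary of any kind is planned. A harms report that follows the plan could therefore understate brief, moderate, provoked dizziness.

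The effect stops at the description of tolerability. Efficacy results do not depend on the rule. Participants remain protected in sessions by the harness, verbal checks and rest breaks. Dizziness longer than 15 minutes or of 7/10 or more is still captured, as are the other listed AEs. It would go too far to say that participants are put at risk or that the trial's conclusions on symptoms or verticality are biased.

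This rests on two assumptions: whole-number ratings, which affect only the naming of 4, 5 and 6 (on a continuous scale the gap is above 3 and below 7), and the absence of a symptom field in the forms and manual that are not reproduced. If such a field exists, only the missing table remains.

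**What to change.** Keep the 7/10 AE cut-off. At each visit, record peak dizziness intensity (0 to 10) and its duration. Add to Statistical Methods one table that shows these values together with the AEs, by group and by session. The cost is two form fields and one table, or the table alone if a form already holds the two items.

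If visits are complete, which the past tense in parts of the protocol leaves open, and the data were not kept, add one sentence to the report: dizziness above 3/10 and below 7/10 lasting 15 minutes or less was not reportable as an AE.

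Lowering the AE threshold to match its stated reason (above 3/10 or longer than 15 minutes) is optional and a matter of judgement. It would probably raise the AE count somewhat, and it is not needed if the table is provided.

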Gait Speed: A 10-meter walk test will be conducted with eyes open and eyes closed in accordance with previously published methodology(39). Participants will be allowed one practice trial for each condition.

Participation Timeline:

Including a telephone screening, there are 9 study contacts over 6 weeks. Questionnaires, as well as tests of verticality perception, balance, and gait are to be collected in weeks 1, 2, 4, and 5 (see Table 2, page 19). The intervention will be conducted 2 times during each twice-weekly visit in weeks 2, 3, and 4. This research is being conducted in the UW-Madison Neuromuscular Coordination Laboratory.

In order to substantially reduce the time each participant is required to be in the lab and increase accuracy of data collection, patient-reported outcomes will be administered via ICTR REDCap. Measures will be collected up to 24 hours before visits 1 and 2, as well as up to 24 hours after visit 3, and up to 24 hours before visit 4 in order to ensure patient-reported and performance-based outcomes are administered at the same time points. Pre-testing with the performance-based outcomes described in this protocol will occur at visit 1 and immediately prior to training during visit 2. Post-testing with the performance-based outcomes will take place immediately after training during visit 7, as well as during visit 8. The intervention will be provided during visits 2 and 3. The data collected at each time point is shown in Table 3.

Participants will be in "on treatment" status during weeks 2-4. "Off study" status coincides with the completion of post-testing.

	Week 0	Week 1	Week 2	Week 3	Week 4	Week 5
Activity						
Screening	Before enrolled					
Outcomes		Baseline 1	Baseline 2		Post-test 1	Post-test 2
Training			2x/week	2x/week	2x/week	

Table 2: Participation Timeline:

Table 3: Data Collected at Each Assessment Timepoint

Measure	Pre-test 1	Pre-test 2	Post-test 1	Post-test 2
VVAS	Х	Х	Х	Х
VRD-25	Х	Х	Х	Х
ABCS	Х	Х	Х	Х
DHI	Х	Х	Х	Х
VAPM	Х			Х
VRBQ	X			X
SVV	Х	Х	Х	Х

RFT	Х	Х	Х	Х
RDT	Х	Х	Х	Х
MBE	Х	Х	Х	Х
FGA	Х			Х
Gait Speed	Х			Х

Sample Size:

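### The SAE rule has no seriousness criterion and is ambiguous for falls outside sessions, and after visit 8 harms are collected only if the participant reports them

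*Combined protocol and SAP*

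**What the plan says.** Under Harms, Serious Risks, the protocol states: "Falls or any injury that occurs while performing tests or interventions will be reported as a serious adverse event (SAE"). No other definition of seriousness appears. Under Common Risks, dizziness does have a threshold: "only prolonged dizziness (>15 minutes) and/or severe dizziness" is to be reported as an AE. Joint pain and muscle soreness are among the potential AEs. The same paragraph has a rule beginning "If a participant reports a prolonged (> 24 hours) of worsened symptoms", which sends the participant to primary care.

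Under Provisions to Address Unanticipated Problems or Complications, the team "conducted continuous monitoring for unanticipated problems, AEs, and SAEs during each study visit". It "also inquired about possible AEs and SAEs that may have occurred between study visits by asking patients to report any symptoms or concerns", and that request extends to events after visits. The Auditing paragraph has SAEs go to the PI at once, AEs reviewed as needed, and both documented in OnCore. Ancillary and Post-trial Care gives participants a contact for reporting study-related sickness or injury.

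Under Participation Timeline, off-study "status coincides with the completion of post-testing". Visit 8 is the last testing visit.

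**The concern.** Seriousness normally describes the consequence of an event. Here it is assigned by what happened and where. The label matters because it decides whether the PI hears at once or the event waits for review as needed. The study is also unmasked and self-monitored, and the PI holds patents related to the device. That is no allegation, only a reason to settle the classification in advance.

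Falls are the trial's public-health rationale, and the training aims to shift reliance from vision to body sensation. A harm summary in which minor in-session injuries count as serious, and the class of a home fall depends on who reads the sentence, would be a weak basis for the next study. Separately, symptoms that persist after the last battery can reach the record only if the participant makes contact.

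**Working it through.** **Step 1: the SAE sentence applied to cases.** The limiting clause can be attached to falls and injuries together (reading A) or to injuries alone (reading B).

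| Event | Reading A | Reading B |
|---|---|---|
| Strap abrasion in a session | SAE | SAE |
| Harmless fall at home | not an SAE | SAE |
| Fracture from a fall at home | not an SAE | SAE, because it was a fall |
| Serious injury at home without a fall | not an SAE | not an SAE |
| Hospital admission, neither fall nor injury | no category | no category |

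Neither column sorts events by seriousness. Reading A leaves out the home fracture. Reading B makes every harmless fall anywhere serious. The first and last rows do not depend on the reading.

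**Step 2: number of visits.** Participation Timeline gives 9 contacts including the telephone screening: 9 − 1 = 8 visits. Built up from the schedule: 1 baseline visit + 6 training visits (2 per week × 3 weeks, visits 2 to 7) + 1 final visit = 8. The payment figures agree: (250 − 50) / 25 = 8. The same section also places the intervention at visits 2 and 3 and ties questionnaires to visits 3 and 4. That conflicts with its own six-session timeline and must be reconciled.

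**Step 3: who asks, and when.**
- Visits 1 to 8: staff monitor at each visit and inquire about the intervals between them. Statistical Methods puts the last assessment one week after training ends, so visit 8 covers the week after visit 7.
- After visit 8: 0 scheduled contacts. Collection rests on participants having been asked to report "symptoms or concerns that may arise between or after study visits". No end date for AE collection is stated.
- Visit 8 repeats all verticality tests, the MBE, the FGA and gait speed (Table 3). The MBE uses 50-second trials, including a rotating annulus, whereas Minimization of Risks describes provocative exposure of about 5 seconds per trial. These passages must also be reconciled.
- Visits without later staff-led inquiry: 1 of 8. Test batteries without it: 1 of 4. This applies to each of 15 + 15 = 30 participants.

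**Step 4: are falls asked about?** Fall history is a screening question. No outcome in the Administrative Information or Table 3 counts falls. The between-visit inquiry is framed as symptoms or concerns, which need not bring out a fall without injury.

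**Step 5: how far the wording alone could move the SAE count.** The documents give no fall rate. Assume 0.5 to 2 falls per person-year in Group 2, and about 4 weeks from visit 1 to visit 8:

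15 × 4/52 = 1.15 person-years
1.15 × 0.5 = 0.6 falls; 1.15 × 2 = 2.3 falls

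Falls between visits would add nothing to the SAE count under reading A and about 0.6 to 2.3 SAEs under reading B. This range measures an unsettled label under an assumed rate. It does not estimate missed events.

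**The case against.** A reader might infer that falls at home go unrecorded. The documents do not support that for the on-study period: staff inquire about AEs and SAEs between visits, and all are documented. That inquiry also presupposes that an SAE can occur between visits, which sits badly with reading A. This part of the objection stands, and it leaves classification as the gap.

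A reader might also set assumed session time (8 visits of 1 to 2 hours, so 8 to 16 of 672 hours, or 1.2% to 2.4%) against time on study and call it the share under surveillance. It is not: it measures the reach of one label under one reading, while the inquiry covers the whole interval. Nor can one say that the rule counts falls where they are least likely. The FGA and the eyes-closed walk are in-session tests with no harness described.

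It can be argued that treating every in-session injury as serious is cautious, that the sentence does not say nothing else is an SAE, and that IRB reporting guidance and Good Clinical Practice apply. Joint pain and muscle soreness are symptoms, so listing them as AEs does not contradict an injury rule. All of this is fair. But caution about minor injuries supplies no category for a serious non-injury event, and neither general reference is said to replace the protocol's own rule.

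After visit 8, participants have been asked to report and have a contact, so later symptoms are not simply lost. The consent pages were not available and may say more. What remains is that the protocol schedules no staff-led contact after that battery.

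**Conclusion.** The point holds as one of definition and follow-up. The SAE rule lacks a seriousness criterion, is ambiguous for falls outside sessions, and gives a serious event that is neither a fall nor an injury no category. Between visits 1 and 8 events can be captured, but falls are not specifically asked about and a home fall has no clear class. After visit 8 collection is passive and has no stated end. That inquiry stops at visit 8 is inferred from the schedule; the protocol does not say so.

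The firm size is one of eight visits and one of four batteries without later staff-led inquiry, in each of 30 participants. The documents give no basis for a number of missed harms. The efficacy analyses are unaffected. The change is worth making because, with 15 symptomatic participants, the class given to one or two events would alter the harm summary.

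**What to change.** 1. Replace the Serious Risks sentence with an outcome-based definition (death, life-threatening event, hospital admission, lasting disability, or other medically important event), applied wherever the event occurs from visit 1.
2. Record every other fall or injury, in the lab or at home, as an AE with its date and the time since the last session.
3. Make the existing between-visit inquiry include one fixed falls and symptoms question at visits 2 to 8.
4. Send that question once through the existing REDCap e-mail more than 24 hours after visit 8, with a paper form for those who declined e-mail. Close AE collection on reply, or at a fixed date if there is none, and state this end separately from off-study status.

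The cost is revised wording, one recurring question, one automated message and a little staff time for paper forms. No lab visit is added. AE collection ends slightly later, and the recorded fall count may rise because falls are now asked about.
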